9.1 Data monitoring

Monitoring visits by a site monitor from Sophia Laboratories, S.A. of C.V. are intended to confirm that the studies sponsored by Sophia Laboratories, S.A. of C.V. they are conducted in accordance

with the ethical principles that have their origin in the Declaration of Helsinki and that are consistent with Good Clinical Practices and with the applicable regulatory requirements (verifying a continuous compliance with the protocol, amendment or amendments, reviewing accounting records of the product under investigation, verifying that the personnel of the site and the facilities remain adequate to carry out the study).

The researcher must ensure that they have sufficient time, space and qualified personnel for the monitoring visits.

In order to carry out the monitoring review, it is mandatory to provide direct access to all source data and those related to the study site. The monitor will conduct a review of the CRF and a Verification of Source Documents (VDF). By VDF means the verification of the records in the CRF through its comparison with the source data that the researcher will make available for this purpose.

Regarding the CRF, the monitor will mark the screens completed and approved at each visit.

In accordance with the applicable regulations, Good Clinical Practices, and the procedures of Sophia Laboratories, S.A. of C.V. The monitors of Sophia Laboratories, S.A. of C.V. they will contact the site before the start of the study to review the protocol, the regulatory and ethical requirements of Laboratorios Sophia, S.A. of C. V. with the staff of the site. When reviewing the procedures for data collection, the conversation will also include the identification, agreement and documentation of the individual data for which the records in the CRF serve as source documents.

Sophia Laboratories, S.A. of C.V. monitor the study to verify, among other things, that:

- The data is authentic, correct and complete.
- They are protecting the security and rights of the subjects.
- The study is being carried out in accordance with the currently approved protocol, any other study agreement, Good Clinical Practices and all applicable regulatory requirements.

The investigator and the head of the medical institution (when applicable) agree to allow the monitor to have direct access to all relevant documents.

Study monitoring visits will be conducted at regular intervals, depending on the recruitment rate, under the arrangements between the investigator and the sponsor. All information related to these visits will be handled as strictly confidential.

Upon completing or discontinuing the study prematurely, the monitor will carry out site closure activities with the investigator or site staff, as appropriate, in accordance with applicable regulations, Good Clinical Practices, and Sophia Laboratories S.A. of C.V. procedures.

After the study is closed, the researcher must keep all study records on the site in a safe place. Records should be maintained to allow easy and timely recovery, when necessary (for example, in an audit or inspection). Sophia Laboratories, S.A. of C.V. will inform the investigator / institution the period of time they will have to retain these records, in order to comply with all applicable regulatory requirements. Nevertheless, the investigator / institution must seek the written approval of the sponsor before proceeding to the elimination of these records. The minimum retention time will satisfy the most stringent standard applicable to that site for the study, in accordance with the provisions of the PCBs, any institutional requirements or the applicable laws or regulations, or the standards / procedures of Sophia Laboratories, S.A. of C.V.

The researcher / institution must notify Sophia Laboratories, S.A. of C.V. of any change in file arrangements including, without limitation, the following: file in an off-site facility, ownership transfer of records in the event the investigator leaves the site.

9.2 Preliminary analysis and early termination of the study

The partial analysis will allow the sponsor to make a decision about the early termination of the study in the event that the safety of the participants is compromised.

The early termination of the study will be considered in the following cases:

1. Presence of serious adverse events in more than 5% of the participants in each intervention group.
2. The competent authority considers it for security alerts.
3. The Sponsor determined it for your convenience or eventualities such as: economic support, manufacturing errors, etc.
4. Lack of recruitment as expected.

In case the decision is the early termination of the clinical study, all the research centers will be informed within the first 24 hours by the available communication channels. Likewise, the corresponding authority in each country will be informed (if applicable) and the Ethics Committees involved.

Each research center has the obligation to inform the subjects that participate in the clinical study in a period no longer than 24 hours, after receiving the information from the sponsor. You must inform all the subjects involved in any phase of the study.

The result of the preliminary evaluation will be in charge of the Clinical Operations Management and the Medical Management of Sophia Laboratories, S.A. of C.V., which will have the faculty to determine the fate of the present protocol, as they deem convenient.

9.3 Adverse events

9.3.1 Investigator's responsibilities

Perform the verification of adverse events through questioning, relevant physical examination, assessment of evolution, as well as adequate medical and pharmacological management, resolution or outcome and final discharge following the definitions determined in national and international regulations. [73] [74] [75]

In case of adverse events or any event that puts the health and well-being of the patients at risk, appropriate medical attention will be provided, either at the research site or will be referred to the Hospital Center with greater resolving power with which the research site and / or researcher have medical care agreement. The researcher will notify the clinical monitor of the sponsor, according to the times established in the national and international regulations. In the case of serious adverse events, notify the sponsor and record the corresponding information in the case report form and in turn inform the Research Ethics Committee, the Research Committee.

The attention of the adverse events will be made according to the diagram of attention of the event (see **Figure 5. Attention of the adverse event**)

In the final report to be drafted by the Scientific Committee of the Department of Clinical Operations of Sophia Laboratories, S.A. of C.V., will include the report of adverse events in compliance with current national and international regulations. [73] [74]

9.3.1.1 Record of adverse events in the Case Report Form

The registry of adverse events considers the information concerning the identification data of the participating patient as code, age, sex, left eye, right eye.

Information about the type of adverse event, adverse reaction or suspected adverse reaction to the product under investigation or to the study medication, as appropriate. The date on which the adverse event occurs is reported, as well as in which the Investigator is aware of it, date of resolution or outcome, as applicable. The clinical diagnosis is indicated. If a lack of therapeutic response is detected to the investigational product and / or investigational medication, it should be reported as an adverse reaction. Include in concomitant medications the therapy used for the pharmacological management of the adverse event, suspected adverse reaction, adverse reaction. Record the outcome or resolution of the event: patient recovered without sequelae, with sequelae, not recovered. Patient who presented death due to adverse reaction / adverse event, patient who presented death and it is judged that the drug could have contributed, patient who presented death and this is not related to the investigational product or drug, or indicate that it was not known what the consequence of the event is.

Consign information about the product or drug under investigation or the drug associated with the adverse event, adverse reaction or suspected adverse reaction. As applicable, information concerning generic denomination, distinctive denomination or product code in research and / or investigational medication should be recorded, as appropriate according to the methodological design of the study, this is relevant in the case of blinded studies or those where they use placebo as comparators, since there are circumstances that justify opening the cecum to determine if the adverse event, the adverse reaction or suspected adverse reaction may be attributable to the active agent, the combination of active agents, or the substance (s). s) pharmacologically inert (s), such as vehicles or additives, as appropriate to the clinical research phase in which the development of the drug is located.

It will also be necessary to record the data concerning a) batch number, b) manufacturer laboratory, c) expiration date, d) dosage, e) route of administration, f) start dates and g) term of administration and / or consumption, reason for the prescription; according to whether it is a product or investigational medicine (protocol in which the patient currently participates) or is a medicine that the subject under investigation consumes for the treatment of basic concomitant diseases or used for the management of any sign or transient symptom that does not correspond to the Natural History of the pathology that motivated its entry into the research protocol.

Record the withdrawal or maintenance of the medication, investigational product or investigational medication, as appropriate. Indicate if the adverse event disappears when the investigational product or investigational medication or suspicious medication is removed (to provoke the event). Also indicate if a dose adjustment is made, if the event changes in terms of intensity or seriousness, persistence of the reaction. It is important to indicate that in those patients who are exposed again to the investigational product, investigational medication or medication, which had previously been suspended, if the adverse reaction or adverse event reappears.

Regarding concomitant pharmacotherapy. Indicate the generic name, the dose, the route of administration, start and end dates of its use, as well as the reason for the prescription regardless if it is consistent with the information to prescribe or technical data sheet or is used outside the regulations or of what the local, national or international regulatory entity has authorized.

Concerning the relevant clinical antecedents. The analysis of the adverse event, adverse reaction or suspicion of adverse reaction considers the information previously reported, notwithstanding the

clinical context in which said harmful phenomenon occurs in the participants of the clinical research protocol, it is of special interest, so that the information about previous ailments, hypersensitivity or allergy phenomena, previous surgical procedures, laboratory analysis or cabinet exams that have been practiced on the participant, etc., that the researcher deems convenient to mention may do so. If you have enough space in the case report format, you can complement the information in your clinical note of the clinical file.

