5.5.3 Secondary objectives

- Evaluate the efficacy of PRO-145 through the decrease of CCA in the ordinal scale during visits
- Evaluate the efficacy of PRO-145 by decreasing the central thickness of the retina (GCR).
- Evaluate the efficacy of PRO-145 by decreasing clinical corneal edema.
- Evaluate the efficacy of PRO-145 through the reduction of conjunctival hyperemia.
- Evaluate the efficacy of PRO-145 by means of the decrease of flare.
- Evaluate the efficacy of PRO-145 in reducing symptoms: pain and photophobia.
- To evaluate the tolerability of PRO-145 by means of the interrogation of ocular symptomatology post-stiffening.

- Evaluate the safety of PRO-145 through the CV, the PIO and the incidence of EA
- To evaluate the efficacy of prednisolone acetate 1% by means of the decrease of CCA in the ordinal scale during visits
- Evaluate the efficacy of prednisolone acetate 1% by means of the decrease in GCR.
- Evaluate the efficacy of prednisolone acetate 1% by means of the decrease of clinical corneal edema.
- Evaluate the efficacy of prednisolone acetate 1% by means of the reduction of conjunctival hyperemia.
- Evaluate the efficacy of prednisolone acetate 1% by means of the decrease in flare.
- Evaluate the efficacy of prednisolone acetate 1% in reducing symptoms: pain and photophobia.
- To assess the tolerability of prednisolone acetate 1% by means of the interrogation of ocular symptomatology postinstillation.
- Evaluate the safety of prednisolone acetate 1% by means of the CV, the PIO and the incidence of EA.

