6.3.4.2 Storage

The medication must be stored in a secure area with restricted access. Storage should be at room temperature to no more than 30 ° Celsius.

The research center has the obligation to record, in the format designated by the sponsor, the temperature and humidity registered in the data logger. This record should include the current temperature and humidity, as well as the minimum and maximum of each of these. It must be done at least once a day, on business days.

Said data will be compared by the clinical monitor according to the registration in the data logger.

6.3.4.3 Return.

The research subjects will return, to the personnel indicated by the IP in the center, their treatments in the final visit.

The refund will be made by the research center when the sponsor indicates it. Prior to the return the research center must make a count of the assigned medication and the remaining medication, with the aim of creating an inventory which serves for the final filling of the medication return form.

6.4 Outcome variables.

6.4.1 Security variables.

6.4.1.1 Primary outcome variables.

Visual ability

Adverse events

Intraocular pressure.

6.4.1.2 Tolerability variables.

Symptomatology postinstillation

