6.5.3 Diagram of the study

[figure not shown]

Figure 4. Diagram of the study

6.6 Sample size.

The sample size calculated for the present study is 178 subjects.

Divided into two intervention groups, each group will be comprised of 89 subjects. Each subject will provide an eye for efficacy analysis.

6.6.1 Calculation of the sample size.

The sample size was calculated using the formula for two proportions variables as well as the data was entered into the online calculator, software developed in: www.powerandsamplesize.com based on Chow S et al. [72]

With a statistical confidence of 95% corresponding to the type I error, equal to 1.96, with a power of 80%, corresponding to the type II error, equal to 0.84. A 78.9% efficiency ratio was considered in the reduction of the degree of cells in the anterior chamber after the application of 4 weeks of difluprednate 0.05% in 79 subjects submitted to phacoemulsification compared to an efficiency ratio of 77.5% with the use of 1% prednisolone. [53]

According to the previous calculation, the result is 74 eyes per group. The total when considering 2 intervention groups is 148 eyes, which was increased by 20% (30 eyes) for the probable losses. The total sample size required is 178 eyes. **Total n = 178 eyes.**

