8.3 Statistical methodology

8.3.1 Analysis of primary and secondary outcome variables

The statistical analysis will be carried out by personnel of Sophia Laboratories. The statistical program SPSS version 19 will be used.

The designated personnel will be blinded to the intervention groups. The coding will be done using consecutive numbers for each intervention group.

The data will be collected and sorted in an excel sheet. Later they will be exported to the platform of the SPSS program. The variables will be categorized according to their nature.

The results of the continuous quantitative variables will be presented in measures of central tendency: mean, standard deviation and ranges. See **Table 5 Variable measurement method**. The total size of the samples will consider an eye as a case for the evaluation of the efficacy.

The normal distribution of results will be obtained through the Kolmogorov-Smirnov and Shapiro-Wilks test, as applicable.

The statistical analysis of the continuous quantitative variables to find significant differences (p) will be the following:

. Inter-group analysis: t test for paired samples.

. Intra-group analysis: Mc Nemar test. Cellularity assessments in the anterior chamber will be considered for the analysis before the application of the intervention and in the final visit. The level of difference to consider significance will be of an alpha of 0.05 or less.

The result of nominal and ordinal qualitative variables will be presented in frequencies, proportions and percentages. See **Table 5 Method for measuring variables**

The statistical analysis to identify significant differences of the qualitative variables will be done by creating 2x2 contingency tables and will be done as follows:

- Difference between groups: χ^2 test (Chi-square) of Pearson or Fisher's exact in expected values less than 5.
- Intra-group analysis: Mc Nemar test.

The level of difference to consider significance will be an alpha of 0.05 or less.

For the reporting of adverse events all eyes of those participants who were randomly assigned to an intervention group will be considered. The results will be expressed in number of cases.

The final report of the results will be shown in tables or graphs, as appropriate.

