8.3.3 Population analysis and management of missing data

The effectiveness analysis will consider those cases in which the measurements of the baseline and final visit are met. Those subjects who do not comply with any of these measurements will not be integrated into the final database to evaluate the effectiveness. Nevertheless, an intention to treat analysis (ITT) will be carried out.

The safety assessment will include in the analysis all those subjects (considering one eye or both) who have been exposed at least once to any of the interventions regardless of the visit in which they were eliminated from the study.

9. Methods Monitoring

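### Lack of therapeutic response is recorded as an adverse reaction and never separated, so adverse event incidence includes efficacy failures and a real difference in adverse events can be diluted

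*Combined protocol and SAP*

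**What the plan says.** Protocol section 9.3.1.1, on recording adverse events in the CRF, says that if a "lack of therapeutic response is detected to the investigational product and / or investigational medication, it should be reported as an adverse reaction". The instruction covers both products. No section defines lack of therapeutic response or gives it a threshold or a time point.

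Adverse events are one of three primary safety variables in 6.4.1.1, with visual ability and intraocular pressure. Section 5.5.3 sets the matching objective for each arm: "Evaluate the safety of PRO-145 through the CV, the PIO and the incidence of EA" and "Evaluate the safety of prednisolone acetate 1% by means of the CV, the PIO and the incidence of EA".

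On analysis, 8.3.1 states: "For the reporting of adverse events all eyes of those participants who were randomly assigned to an intervention group will be considered". It adds: "The results will be expressed in number of cases". Section 8.3.3 bases the safety assessment on all subjects "who have been exposed at least once to any of the interventions regardless of the visit in which they were eliminated from the study". Neither section excludes, flags or separately tabulates lack-of-response records.

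**The concern.** The primary efficacy objective (5.5.2) is elimination of anterior chamber cells at the final visit. An eye that fails to respond can count once as an efficacy failure and again as a safety event. The label also presumes that the drug caused the event, although 9.3.1.4 provides a separate causality assessment.

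Two consequences follow. First, incidence rises in both arms for reasons unrelated to harm, and this added background makes a real difference in ocular adverse events harder to see. That happens even when the arms respond equally well. Second, if the arms differ in response, part of that difference reappears in the adverse event table.

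Because the term is undefined, sites may also apply it differently across visits, so the amount of added background could vary by centre.

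**Working it through.** **Inputs from the protocol.** The planning response rates in 6.6.1 are 78.9% for difluprednate ("A 78.9% efficiency ratio was considered in the reduction of the degree of cells in the anterior chamber") and 77.5% for prednisolone. Group size is 89. Two-sided alpha is 0.05 (z = 1.96).

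**The plan's own figures.** The protocol computes nothing for adverse events. The enrolment total reproduces from its last step: 148 × 1.2 = 177.6, rounded up to 178, or 89 per arm. The 74 per arm behind it does not reproduce as a test of 78.9% against 77.5%, which would need 13,653 per arm. That is a separate matter, and nothing below depends on it.

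**Assumptions.** The protocol gives no expected adverse event rates, so the true rates are assumed. Adverse events are treated as the proportion of subjects with at least one event. Reported non-response is taken as independent of true events.

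**Recorded rate.** With true rate b and a share r of subjects reported for lack of response:

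recorded rate = 1 − (1 − b)(1 − r)

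**Upper bound for r.** If every planning non-responder were reported:
- PRO-145: 89 × (1 − 0.789) = 18.8 subjects (21.1%)
- prednisolone: 89 × (1 − 0.775) = 20.0 subjects (22.5%)

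These average to about 22%.

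**Dilution.** The same r is applied to both arms, so no efficacy difference is involved. Power = Φ{(d − 1.96·SE₀)/SE₁}, where d is the difference in recorded rates, SE₀ = √[2p̄(1 − p̄)/89] and SE₁ = √{[p₁(1 − p₁) + p₂(1 − p₂)]/89}.

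True rates assumed 5% and 15%:

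| Share reported (r) | Recorded rates | Difference (points) | Power |
|---|---|---|---|
| 0 | 5.0% vs 15.0% | 10.0 | 0.61 |
| 2% | 6.9% vs 16.7% | 9.8 | 0.53 |
| 5% | 9.75% vs 19.25% | 9.5 | 0.44 |
| 10% | 14.5% vs 23.5% | 9.0 | 0.33 |
| 22% (upper bound) | 25.9% vs 33.7% | 7.8 | 0.20 |

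Last row in full: p̄ = 0.298, SE₀ = 0.0686, SE₁ = 0.0683, and (0.078 − 1.96 × 0.0686)/0.0683 = −0.83, so power is about 0.20.

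With assumed true rates of 5% and 20%, power falls from 0.86 with no reporting to 0.39 at r = 22% (recorded 25.9% vs 37.6%).

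**Bias between arms.** With the same true rate b in both arms and every planning non-responder reported, the recorded rates differ by (1 − b)(0.789 − 0.775):
- b = 5%: 0.95 × 0.014 = 1.3 points
- b = 10%: 0.90 × 0.014 = 1.3 points (28.99% vs 30.25%)
- b = 30%: 0.70 × 0.014 = 1.0 point

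A larger bias needs a larger efficacy gap. With assumed response of 85% vs 70% and b = 10%, the recorded rates are 1 − 0.9 × 0.85 = 23.5% and 1 − 0.9 × 0.70 = 37.0%. The protocol does not plan for such a gap.

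**The case against.** The strongest objection concerns size. The planning rates describe a reduction in cell grade and, as 5.3.1.4 indicates, come from a paediatric trial. The efficacy objective is elimination of cells in adults. An eye that improves from 3+ to ½+ has not cleared, yet few investigators would report it as a lack of response. Reading 6.6.1 as implying 19 or 20 such reports per arm therefore goes beyond the text. This stands: 22% is an upper bound, and the realistic share is unknown.

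A reader might infer that the less effective arm will look less safe. The protocol's own rates do not support that as a general statement, because the shift they imply is about 1 point. It would be material only with a real gap in response.

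A reader might also infer that the whole safety evaluation is compromised. It is not. Intraocular pressure, visual ability and post-instillation symptoms are measured separately, and 9.3.1.1 does not alter them. The early termination rule in 9.2 counts serious events only, so it is affected only if a lack-of-response report is also serious.

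The protocol names no specific test for adverse events and reports them as case counts, although 5.6.1 intends a comparison of safety profiles. The power figures therefore measure lost sensitivity, not the power of a planned test.

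Finally, the CRF records event type and clinical diagnosis, so the records could be separated later. That makes the repair easy but does not put it in the plan. A split chosen after the data are seen would be open to challenge.

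**Conclusion.** The concern holds as a defect in how adverse events are recorded and tabulated. Followed as written, the protocol puts efficacy failures into adverse event incidence in both arms and has no rule for taking them out. The main effect is dilution. In the assumed 5% vs 15% case, power falls from 0.61 to 0.53 if 2% of subjects are reported, and to 0.20 at the 22% upper bound. Bias between arms is limited to the difference in response, about 1 point at the planning rates.

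These sizes rest on assumed true adverse event rates, on an unknown reporting share, and on independence between non-response and true events. The existence of the problem rests on none of them, since it follows from the text of 9.3.1.1, 8.3.1 and 8.3.3. The primary efficacy analysis is not touched. The change should be made because it is cheap and a stated safety objective depends on it.

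**What to change.** - **9.3.1.1:** keep any report that pharmacovigilance rules require. Define lack of therapeutic response for reporting purposes, and flag it in the CRF under its own code (lack of effect).
- **8.3.1:** state that the main incidence of adverse events and adverse reactions is tabulated without lack-of-effect records. Add a second tabulation that includes them and a listing by arm.
- **Complications of inflammation:** state that these remain adverse events under their own diagnosis.

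Showing both tabulations is safer than excluding the records outright, because the national rules that the protocol cites cannot be checked here. The cost is a few sentences, one CRF flag and one extra table or listing. Visits, treatment and sample size do not change.
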